ART	Antiretroviral therapy
AUDIT-C	Alcohol Use Disorders Identification Test – Consumption
CRF	Case report form
Grade 3/4 hepatotoxicity	ALT or ALT >3 x ULN and symptoms (nausea, vomiting, jaundice, or fatigue) OR ALT or AST >5 x ULN
NIAAA heavy drinking	Men: ≥ 4 drinks/day or ≥ 14 drinks/week; Women: ≥ 3 drinks/day or ≥ 7 drinks/week
INH	Isoniazid
IPT	Isoniazid preventive therapy
EMM	Electronic medication monitoring
PEth	Phosphatidylethanol
TST	Tuberculin skin test
ULN	Upper limit of normal

Alcohol users are considered at high risk for INH-related hepatotoxicity, based on an early study of IPT in which any and daily alcohol use were associated with 2- and 4- fold increases in toxicity rates, respectively.⁴⁵ However, the high rates of toxicity in this study have since been questioned.⁴⁶ Only a handful of studies since this 1978 publication have reported INH-related toxicity stratified by alcohol consumption level, and the findings of these subsequent studies have been mixed.^{26,47-51} Thus, data are urgently needed on the safety and tolerability of TB preventive therapy in HIV-infected drinkers to inform worldwide guidelines.⁵²

Adherence to TB preventive therapy among drinkers on ART is unknown. Among those with HIV, alcohol use has been consistently associated with reduced ART adherence,^{22,53,54} and we ([name]) and others have found that alcohol use is associated with discontinuation of active TB treatment.^{23,48,55} Reports of adherence to IPT among all comers range widely, from 19-96%.^{52,56} While completion of 9-months of IPT in a study of persons with HIV in Uganda was 34%,⁵⁶ several studies in HIV-infected persons have shown good completion rates (82%-87%), with the highest rates among those on ART.^{41,57-59} The addition of IPT to an established pill taking routine may be feasible, but adherence to and completion of TB preventive therapy among HIV-infected drinkers on ART is not known.

Valid measurement of medication adherence is critical to evaluating IPT. A key component of the scale up of TB preventive therapy for persons with HIV will ultimately be medication adherence. Self-reported adherence measures have limitations,⁶⁰⁻⁶³ especially in settings in which socially desirable responses are likely to be high. This problem was recently illustrated by the lack of efficacy of pre-exposure prophylaxis for HIV in a large trial, due to patients' misreporting taking the prescribed antiretrovirals.⁶⁴

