C.3.12 Aims 1 and 2 potential pitfalls. It is possible that our hepatotoxicity and treatment discontinuation estimates will be lower than in settings where baseline ALT/AST screening is not performed because we will exclude those with baseline elevations (>2x ULN). Based on our prior work (see C.2), we expect only a small proportion will be screened out. However, using the number screened out, we will be able to calculate "worst case scenario" hepatotoxicity rates assuming that these HIV-infected drinkers would have developed Grade 3/4 toxicities while on treatment. It is also possible that adherence rates in the study will be artificially high, due to the frequent adherence and toxicity monitoring. In that case, our estimates of adherence will represent the upper bound, while the comparison of adherence between the two randomization arms will remain important. If

we establish safety without frequent monitoring, then future studies could measure adherence under more real-world conditions.

C.4 Study methods for Aim 3.

Aim 3: To determine whether the benefits of providing TB preventive therapy to HIV-infected drinkers in resource limited settings outweigh the risks compared to no treatment. We hypothesize that providing TB preventive therapy will result in longer life expectancy and quality-adjusted life expectancy than not providing TB preventive therapy (current standard of care).

C.4.1 Overview. We will utilize our previously developed Markov model that simulates TB preventive therapy and the lifetime clinical progression of a cohort of hypothetical individuals.³³ We will modify this model to fit the Ugandan context by including a detailed simulation of TB preventive therapy safety monitoring. We will then leverage the unique toxicity, tolerability, and adherence data collected in Aims 1 and 2, as well as the medical literature, to project long-term outcomes, stratified by level of alcohol consumption, assuming a variety of monitoring approaches. If our hypothesis is correct, this study will provide evidence needed to change the paradigm of TB preventive therapy and extend life-saving treatment to a population at very high risk of death from HIV/TB co-infection. Below we describe the proposed approach.

C.4.2 Model components. The following model components are part of our previously developed model and will be modified for the context of HIV-infected drinkers in Uganda as described.

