TB epidemiology. The simulation model generates a cohort using the distribution in the target population of age, sex, prevalence of positive TSTs (>5 mm induration), and prevalence of sub-clinical (asymptomatic, so not identified) active TB. We will stratify all demographic and epidemiologic parameters by level of self-reported alcohol use at baseline, as above (any current drinking, heavy drinking, and very heavy drinking – see C.3.9), using the AUDIT-C that is available to treating clinicians in the real-world.

TB preventive therapy. The simulation of TB preventive therapy includes treatment discontinuation due to hepatotoxicity, as well as poor adherence or default. The model is structured to simulate any TB preventive treatment regimen. All parameters related to TB preventive therapy are regimen-specific and we will stratify them by level of alcohol use. We will model the benefits of TB preventive therapy as a relative reduction in the

Table 4: Select model parameters for decision model proposed in Aim 3.

	Parameter estimates	Data source
TB epidemiology		
Age/sex demographics		ADEPTT
Prevalence reactive TST		ADEPTT
Prevalence subclinical TB at baseline	0.085-0.094	135,136
Level of alcohol use prior to therapy		ADEPTT
TB preventive therapy		
Transitions between AST/ALT categories		ADEPTT
Probability of symptoms by AST/ALT	0.35	137
Toxicity-related mortality by AST/ALT	0.0-0.05	137-139
Adherence		ADEPTT
Health state utility for those with hepatotoxicity	0.65-1.0	140
Health state utility for those w/o hepatotoxicity	0.82-1.0	140
Progression to TB and TB mortality		
Incidence TB (per 100 person-years)		141-143
TST positive	3.41	
TST negative	3.06	
Hazard ratio for active TB		144-147
100% adherence vs. no therapy	0.11-0.41	
Partial (50%) therapy vs. no therapy	0.25-0.91	
TB-related case-fatality proportion	0.23	148
Health state utility with active TB	0.66-0.85	140
HIV and other non-TB mortality		
Life expectancy (starting age 31) CD4 >500	66 years	149-152
Standardized mortality ratio by CD4 count		151-154
CD4 350-499 cells/mm ³	3.5	
CD4 200-349 cells/mm ³	5.6	
CD4 <200 cells/mm ³	30.3	
Health state utility for HIV-infected persons	0.62-1.0	155-157

rate of progression to active TB. In the model, patients with sub-clinical TB do not benefit from the preventive therapy.

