Adherence and treatment default. In each month while taking TB preventive therapy, simulated individuals have a probability of non-adherence and/or treatment default, i.e. treatment discontinuation that is unrelated to hepatotoxicity. Simulated patients who stop medications do not accrue the full benefit of prevention, though incomplete courses of therapy confer partial preventive benefits.²¹ One challenge to incorporating treatment adherence data in a decision analytic model is that the effectiveness of various levels of adherence to TB preventive therapy is not known. We will therefore model discontinuation/default and low adherence in two ways: First, we will use WHO definitions of treatment loss to follow-up for active tuberculosis treatment to model TB preventive therapy adherence as a binary outcome (yes/no).⁹ We will define "not adherent" as any patient who misses two consecutive monthly refill visits, or who, for 2 consecutive months, self-reports taking <80% of his/her intended doses of therapy, or whose EMM cap data indicates <80% of doses taken. In the simulation model, individuals will not accrue any benefits (or risks) of therapy after the month that the patient is classified as "non-adherent." Second, we will use EMM adherence data to model non-adherence as a continuous outcome. We will assume that taking fewer than the total number of TB preventive therapy doses throughout the entire course of therapy has the same effect as taking 100% of doses for fewer months than recommended. For example, we will assume that taking 50% of doses for six months of therapy provides similar treatment efficacy as taking 100% of all doses for only 3 months. We will compare the results of these two strategies and thus gain information on the relative importance of how adherence is modeled.

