Progression to active TB and death. Individuals in the simulation model will have a monthly probability of developing active TB that is stratified by drinking status.^{141,158} Those who develop active TB experience increased mortality and decreased quality of life. In addition, a portion of simulated patients with active TB will develop drug resistant disease, characterized by longer treatment courses, higher mortality, and lower quality of life than drug sensitive disease. We will model the effectiveness of TB preventive therapy as a relative reduction in the rate of developing active TB. A complete course of 6H provides a 30-50% reduction in reactivation,⁴⁻⁸ with a larger absolute reduction in TB incidence among those who have reactive TST than in those who do not. Studies among HIV-infected persons in settings of TB incidence, similar to Uganda, demonstrate that the benefits of TB preventive therapy are durable for five years.^{145,159} We will therefore model a 5-year reduction in the incidence of active TB, followed by a rapid return to the baseline TB incidence.

Competing risks of death Individuals in the existing model have an age- and sex-stratified risk of death from causes other than TB. In this proposed analysis of TB preventive therapy in HIV-infected persons in Uganda, the competing risks of death will reflect mortality related to HIV infection and all other non-TB mortality.

C.4.3 Data sources for the model. Whenever possible, we will use the novel data from Aims 1 and 2 of this study (Table 4, denoted as ADEPTT) for model parameters. Other model parameters will be obtained from the medical literature.

TB epidemiology. The ADEPTT cohort will inform the age and sex distributions, and the prevalence of reactive TST (>5 mm) at baseline and level of self-reported alcohol use. We will use published reports of the prevalence of subclinical TB from established African cohorts.^{135,136}

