TB preventive therapy. The ADEPTT study includes frequent assessment of ALT/AST and symptoms. These data, stratified by level of self-reported alcohol consumption, will inform all of the parameters governing movement between toxicity-related health states. Because the study will stop treatment at the identification of any Grade 3/4 hepatotoxicity, we anticipate no medication-related deaths in ADEPTT. Therefore, we will use the medical literature to inform mortality from each toxicity-related health state in the model, as well as the health state utility of patients with toxicity-related symptoms.¹³⁷⁻¹⁴⁰

Progression to active TB and death. Because the number of observable cases of active TB in the cohort after therapy is expected to be low, we will use the medical literature to inform the incidence of active TB, stratified by TST status, without preventive therapy,¹⁴¹⁻¹⁴³ and will account for the reported efficacy of TB preventive therapy.¹⁴⁴⁻¹⁴⁷ We will use reports of health state utility with active TB collected in SSA.¹⁴⁰

Competing risks of death. We will estimate mortality from all causes other than TB using long-term follow-up of cohorts of HIV-infected persons in SSA. We will use the literature to estimate non-TB mortality among a cohort of HIV-infected persons on ART in SSA with baseline CD4>500¹⁴⁹⁻¹⁵² and published reports of the HR for mortality by lower CD4 counts.¹⁵¹⁻¹⁵⁴ We will also use the medical literature to estimate health state utilities for HIV-infected individuals with and without TB.

C.4.4 Aim 3 analyses. We will use the model to simulate the long-term outcomes of a cohort of HIV-infected drinkers in Uganda with demographic and clinical characteristic similar to those of the ADEPT-TB cohort assuming that TB preventive therapy is provided to all HIV-infected patients who drink alcohol using each of the following TB preventive therapy and monitoring strategies:

- (1) No therapy (standard of care)
- (2) TB preventive therapy without hepatotoxicity monitoring unless patient is symptomatic (no monitoring)
- (3) TB preventive therapy with hepatotoxicity monitoring at week 2 of therapy only (week 2 monitoring)
- (4) TB preventive therapy with hepatotoxicity monitoring monthly throughout (monthly monitoring)

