The simulated model outcomes will include: hepatotoxicity events and deaths, counts of treatment completion and non-adherence, cases of active TB, TB deaths, life expectancy, and quality-adjusted life expectancy. We will first compare life expectancy and quality-adjusted life expectancy for “no monitoring” to “no therapy” to determine whether TB preventive therapy provides net benefit to HIV-infected drinkers even when monitoring is simply not possible. Next, we will compare outcomes from “no monitoring,” “week 2 monitoring” and “monthly monitoring”, to identify the optimal monitoring approach in settings that have some ability to monitor liver functions tests. We will define the “optimal” approach as that which maximizes quality-adjusted life expectancy. Once we have modeled outcomes for the simulated cohort, we will investigate whether the approach to TB preventive therapy should differ based on level of drinking alcohol. We may find, for example, that no monitoring is needed for non-heavy drinkers, while it is necessary for heavy and very heavy drinkers.

C.4.5 Sensitivity analyses. We will use one- and two-way deterministic sensitivity analyses to test the role of uncertainty in driving conclusions and to identify model parameters that have the largest impact on outcomes. We will display the results of such deterministic sensitivity analyses in standard format, such as tornado diagrams and two-way sensitivity graphs.¹⁶⁰⁻¹⁶² Next, we will use probabilistic sensitivity analysis (PSA) to quantify the impact of simultaneous uncertainty in all model parameters on the qualitative conclusions of the analysis.^{160,163} PSA defines every model parameter as a probability density function centered around the best estimate of that parameter’s true value. PSA then performs thousands (typically 10,000) of iterations of the simulation, each time drawing a value for each model parameter from its defined probability density function. The end result is N (10,000) realizations of the simulation, each with its own life expectancy and quality-adjusted life expectancy. By comparing the percentage of the simulations whose conclusions concurred with the base case scenario, it is possible to quantify the degree of certainty in the conclusions of the analysis. Model parameters that will be inherently uncertain and candidates for PSA include the efficacy of TB preventive therapy, the rate of reactivation of TB, and the impact of less than perfect adherence.

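### Aim 3 uses ADEPTT adherence for every treated strategy, although C.3.12 warns that it may be inflated by monitoring; the benefit of therapy in routine care may be overstated

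*Combined protocol and SAP*

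**What the plan says.** C.4.3 sets the data rule for the Aim 3 model: "Whenever possible, we will use the novel data from Aims 1 and 2 of this study (Table 4, denoted as ADEPTT) for model parameters". Table 4 gives ADEPTT as the source for adherence. C.4.2 adds "Second, we will use EMM adherence data to model non-adherence as a continuous outcome", alongside a binary version built on missed refills and on self-reported or EMM dose-taking below 80%.

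C.4.2 also states what the therapy parameters depend on: "All parameters related to TB preventive therapy are regimen-specific and we will stratify them by level of alcohol use". Monitoring strategy is not named there. In the hepatotoxicity part of C.4.2, monitoring matters through whether a raised ALT/AST is recognised.

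C.4.4 compares no therapy, no routine liver monitoring, one test at week 2, and monthly testing. The first comparison, no monitoring against no therapy, is meant to show whether therapy gives net benefit where monitoring cannot be done.

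On the quality of the adherence data, C.3.12 says: "It is also possible that adherence rates in the study will be artificially high, due to the frequent adherence and toxicity monitoring". It continues: "In that case, our estimates of adherence will represent the upper bound". Real-world adherence is left to future studies. C.4.5 plans one- and two-way deterministic analyses and a probabilistic sensitivity analysis (PSA), of which it says: "PSA defines every model parameter as a probability density function centered around the best estimate". C.4.6, the list of Aim 3 pitfalls, does not mention adherence to preventive therapy measured under monitoring.

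**The concern.** The trial measures adherence with visits at week 2 and months 1 to 7 (C.3.6), pill counts and electronic caps. Aim 3 then asks what would happen in settings without that apparatus. C.3.12 recognises that the two may differ and in which direction, but the model section gives one adherence source for all treated strategies and no downward adjustment.

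The possible error runs one way. If routine-care adherence is lower, fewer TB cases are averted than the model reports. A PSA spreads uncertainty around its centre; if the centre is too high, so is the average of the simulated benefit. The adherence-related PSA candidate named in C.4.5 is the effect of imperfect adherence on outcome, which is a different quantity from how low adherence may fall outside the trial. For toxicity, C.3.12 plans a worst-case calculation; adherence has no counterpart. At stake is the size of benefit reported to guideline bodies for unmonitored therapy.

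**Working it through.** The plan states no Aim 3 result, so there is no figure to reproduce. The following is an illustration from its own inputs.

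**Inputs.** Table 4: TB incidence in TST-positive persons without therapy, 3.41 per 100 person-years; HR at full adherence 0.11–0.41 (midpoint 0.26); HR at 50% therapy 0.25–0.91 (midpoint 0.58); TB case fatality 0.23; toxicity mortality 0.0–0.05. C.4.2: benefit lasts 5 years. C.3.9: expected Grade 3/4 hepatotoxicity 2.6%, upper confidence limit 6.4%. Assumed, because the plan gives neither figure: ADEPTT adherence 90%; routine-care adherence 90%, 70% or 50%.

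**Formulas.** For adherence *a* of at least 0.5, HR(*a*) = HR50 + [(*a* − 0.5)/0.5] × (HR100 − HR50). TB cases per 1000 over 5 years = 1000 × [1 − exp(−0.0341 × HR × 5)]. Competing mortality, drug resistance and utilities are left out.

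**TB cases averted.** With no therapy there are 1000 × [1 − exp(−0.1705)] = 156.8 cases. At the midpoint HRs, 90% adherence gives HR = 0.58 − 0.8 × 0.32 = 0.324, 53.7 cases and 103.0 averted; 70% gives HR = 0.58 − 0.4 × 0.32 = 0.452, 74.2 cases and 82.6 averted. The ratio is 103.0/82.6 = 1.25.

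| HR at 100%; 50% | Averted at 90% / 70% / 50% | Overstated if truth is 70% | If truth is 50% |
|---|---|---|---|
| 0.11; 0.25 | 133.5 / 124.2 / 115.0 | 7% | 16% |
| 0.26; 0.58 | 103.0 / 82.6 / 62.6 | 25% | 65% |
| 0.41; 0.91 | 73.5 / 42.7 / 13.0 | 72% | 5.6-fold |

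If the truth is 90%, the overstatement is nil. Log-linear interpolation gives the same direction.

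**Net deaths averted per 1000.** This is cases averted × 0.23, less toxicity deaths of 1000 × 0.026 × 0.05 × *a*. At 90% / 70% / 50% adherence it gives 29.5 / 27.7 / 25.8 (low HRs), 22.5 / 18.1 / 13.8 (midpoint) and 15.7 / 8.9 / 2.4 (high HRs). The sign changes in only one corner: the high HRs, 50% adherence, 6.4% toxicity, 5% mortality and toxicity not reduced by lower adherence, where 13.0 × 0.23 − 3.2 = −0.2.

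**Link to the completion figures in Background.** That section reports 34% completion of a nine-month course in one Ugandan study and 82%–87% in others. If non-completers take half their doses (an assumption), 34% completion is 0.34 + 0.66 × 0.5 = 67% of doses, and 82% is 0.82 + 0.18 × 0.5 = 91%. At midpoint HRs the TB reduction is 0.34 × 0.74 + 0.66 × 0.42 = 0.529 for the first and 0.82 × 0.74 + 0.18 × 0.42 = 0.682 for the second, against 0.676 at 90% of doses. The overstatement is 0.676/0.529 = 1.28, or 28%, with the first and nil with the second.

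**A related inconsistency.** C.4.2 gives a complete course a 30–50% reduction, whereas the Table 4 HRs of 0.11–0.41 imply 59–89%. With the C.4.2 figures and effect proportional to adherence, 90% against 70% gives 39.7 v 30.7 and 67.2 v 51.9 cases averted, about 29% in each case.

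**The case against.** Five points can be made for the plan.

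- **The upper bound is conditional.** A reader might infer that the plan admits its adherence is inflated. It says only that this is possible, and describes what would follow. That stands: the benefit may be overstated, and no more can be claimed.
- **Sensitivity analyses are already planned.** C.4.5 covers all parameters, its list of PSA candidates is not exhaustive, and adherence is modelled two ways. This stands in part. The deterministic analyses could vary adherence, but no range or downward scenario is prespecified, and a PSA centred on ADEPTT keeps the shift.
- **Two kinds of monitoring are easily confused.** Strategy (2) is "TB preventive therapy without hepatotoxicity monitoring unless patient is symptomatic (no monitoring"), which means no routine liver tests. C.3.12 blames adherence and toxicity monitoring together, and routine monthly liver testing need not include electronic caps or study pill counts. A reader might infer that only the no-monitoring and week-2 strategies are flattered. Nothing in the document isolates an effect of liver tests on adherence, so any inflation could affect all treated strategies.
- **The 34% figure is a poor comparator.** It concerns a nine-month course, while this trial gives six months to patients on ART, and Background says completion was highest in those on ART. This stands: 34% is a stress value.
- **The model stops risks as well as benefits at non-adherence, and credits partial courses.** This also stands, and explains why net deaths averted stay positive in nearly every combination above. A reader might infer that the conclusion in favour of therapy would reverse; these figures do not show that.

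**Conclusion.** The point holds as a gap in the Aim 3 analysis plan. Adherence that the plan itself suspects may be too high is the only source given for all treated strategies, and the planned PSA would not correct a one-sided shift. Lower adherence reduces TB cases averted over the whole Table 4 HR range, so the direction is clear if monitoring does raise adherence. The size is not known: about 25% at the midpoint HRs for 90% v 70% (7% to 72% over the range), and nil if routine-care adherence equals ADEPTT adherence. These figures rest on assumed adherence levels, linear interpolation of the HR and a model without competing mortality. They concern the size of the benefit; they do not show that its sign is wrong.

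**What to change.** Keep ADEPTT adherence as the base case and add the following to C.4.5.

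1. A prespecified routine-care scenario that shifts adherence downward for all treated strategies. Take the range from the Background literature, for example 34% to 87% completion, with 34% labelled a stress value because it is for a nine-month course. State how completion is converted to doses taken.
2. Apply the shift to both TB benefit and toxicity exposure.
3. Report the break-even adherence at which no monitoring stops beating no therapy, or state that none was found in the range.
4. Treat any difference in adherence between monitoring strategies as a labelled sensitivity analysis only.

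EMM data after day 40, already planned in C.3.10, can be shown as an intermediate case. They are still collected under monitoring, so they cannot stand in for routine care. Separately, reconcile the efficacy figures in C.4.2 and Table 4, since the size of the scenario effect depends on them.

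The cost is a few more model runs and no new data; the reported benefit may be smaller.

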C.3.5 Intervention. The study intervention will include a single arm given (1) 6H: 300 mg INH daily for 6 months. All participants will also receive 25 mg pyridoxine (vitamin B-6) daily for the treatment duration to reduce the risk of INH-induced peripheral neuropathy.¹¹¹ Patients will be encouraged to continue taking all other concurrently prescribed drugs (i.e., ART and cotrimoxazole). Patients will receive adherence advice, advice to avoid hepatotoxic substances (e.g. acetaminophen, alcohol, herbal medicines), instructions on monitoring side effects, phone numbers for contacting the medical staff in case of serious side effects, and instructions on using the EMM bottle like a regular medicine bottle. The pills will be dispensed at the pharmacy where the participants receive their ART.

C.3.6 Follow-up study visits. Assessments for toxicity will occur week 2 and months 1 through 7 (Table 3). A clinical officer will screen for symptoms of hepatotoxicity and other side effects using a Case Report Form (CRF) based on the TEMPRANO ANRS adverse event grading⁶ and perform ALT/AST testing. Treatment will be stopped if a patient develops a Grade 3/4 toxicity, as determined by the study physician. In addition, the monthly study visits while on medication will include pharmacy pill counts, EMM data downloads, and brief surveys on alcohol use and adherence. Hair collection will occur at 3 and 6 months. Blood collection will occur at baseline (for PEth, CD4 cell count, HIV viral load, and repository storage), 3 and 6 months, and every 6 months thereafter. Participants will also be given a card with phone numbers to contact the clinical staff if side effects occur between study visits; if side effects occur, participants will be asked to come in for additional ALT/AST testing and follow-up. These calls and visits will also be recorded in a CRF. All CRFs will be reviewed weekly by the study physician. Screening for symptoms for active TB, and sputum testing and chest X-ray if symptoms are reported, will occur at every follow-up visit, including those after the completion of the trial. High retention will be maintained as in our prior studies using follow up phone calls, alerts when patients come to the ISS clinic, and home visits when needed.

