Hepatotoxicity. We will substantially enhance our previous model to include detailed simulation of preventive therapy as follows: First, in every treatment month, simulated individuals on therapy will have a probability of developing an ALT or AST elevation and a probability of developing symptoms of hepatotoxicity. Simulated patients will fall into one of 6 toxicity-related health states (3 levels of ALT/AST levels; normal, 3-5x the ULN, >5x ULN) and 2 levels of symptoms (yes/no). The rates of movement between each of the 6 hepatotoxicity states will be a function of the treatment regimen, and an individual's level of alcohol consumption. Each toxicity-related state will be associated with toxicity-related quality of life, and mortality.

Importantly, the model will distinguish between the underlying true ALT/AST value and the clinical awareness of that value. For example, in the simulation model of no monitoring, patients without symptoms whose true ALT/AST is >5x ULN will not be identified, nor their treatment stopped, and they will have an increased risk of developing symptoms and death.

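### Aim 3 takes all movement between toxicity states from ADEPTT, but ADEPTT stops INH at any detected ALT/AST above 5x ULN and so cannot show on-drug recovery from that state

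*Combined protocol and SAP*

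**What the plan says.** C.4.3 (TB preventive therapy) says the ADEPTT ALT/AST and symptom data, by level of self-reported drinking, "will inform all of the parameters governing movement between toxicity-related health states". Table 4 also lists ADEPTT, with no value or citation, as the source for transitions between ALT/AST categories.

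Table 1 defines Grade 3/4 hepatotoxicity as "ALT or ALT >3 x ULN and symptoms (nausea, vomiting, jaundice, or fatigue) OR ALT or AST >5 x ULN". Section C.3.6 says "Treatment will be stopped if a patient develops a Grade 3/4 toxicity, as determined by the study physician".

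The model (C.4.2, Hepatotoxicity) has six states: three ALT/AST levels, each with or without symptoms. For the no-monitoring strategy it states that "patients without symptoms whose true ALT/AST is >5x ULN will not be identified, nor their treatment stopped". The same section then describes the outlook for this unidentified group: "they will have an increased risk of developing symptoms and death". C.4.4 compares no therapy, no monitoring unless symptomatic, a single test at week 2, and monthly monitoring.

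C.4.3 recognises one consequence of the stopping rule: "Because the study will stop treatment at the identification of any Grade 3/4 hepatotoxicity, we anticipate no medication-related deaths in ADEPTT". For that reason "we will use the medical literature to inform mortality from each toxicity-related health state in the model", and the utilities of symptomatic patients come from the literature too. On-drug recovery and persistence are not mentioned.

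**The concern.** The model needs to know what happens to a patient with asymptomatic ALT/AST above 5x ULN who goes on taking INH. The trial is designed so that this is not followed once detected. Every planned reading after detection is off drug, so the only exits from this state that ADEPTT can supply are post-stop exits. This is a matter of identifiability, and enrolling more participants would not cure it.

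The error can run either way. The Background says most INH liver injury reverses when therapy stops. If post-stop exits served as on-drug exits, time in the severe state would be understated, which favours no monitoring and week-2 monitoring over monthly monitoring. If on-drug exits were assumed never to occur, time could be overstated, which counts against those two strategies. C.4.4 chooses the optimal monitoring approach by quality-adjusted life expectancy and may conclude that some drinkers need no monitoring. That choice depends on this state.

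**Working it through.** **Which states are affected.** Setting the Table 1 definition against the six model states:

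| ALT/AST level | No symptoms | Symptoms |
|---|---|---|
| Normal | INH continues | INH continues |
| 3-5x ULN | INH continues | INH stopped |
| >5x ULN | INH stopped | INH stopped |

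Three of the six states trigger a stop in ADEPTT. Strategy 2 investigates symptomatic patients, so the stopped state that it clearly keeps on drug is asymptomatic >5x ULN. Strategy 3 does the same for elevations that arise after week 2.

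**How many entries to expect.** Section C.3.9 gives 200 drinkers, 90% retention and a 2.6% rate. So 200 × 0.90 = 180, and 180 × 0.026 = 4.68, or about 5. The exact 95% interval for 5/180 is 0.91% to 6.36%, which matches the stated 0.9% to 6.4%. Some of these events will be symptomatic, and they are then split by drinking level. Planned on-drug follow-up after detection is zero.

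**Illustration of size.** The recovery rates are assumptions, and Table 4 gives no time units. Let r be monthly recovery, s the monthly probability of symptoms and d monthly mortality. The probability of staying in the state for another month is q = (1 − r)(1 − s)(1 − d). With n on-drug months left, mean time in state is the sum of q^j for j = 0 to n − 1. I took d = 0.05, the top of the Table 4 range, read as monthly. Example: s = 0.35 and r = 0.5 give q = 0.5 × 0.65 × 0.95 = 0.309.

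- Case A: s = 0.35 read as monthly, n averaged over 1 to 6.
- Case B: s = 0.35, n = 5.
- Case C: 0.35 read as a six-month probability, s = 1 − 0.65^(1/6) = 0.069, n averaged over 1 to 6.

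Mean months in state:

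| Case | r=0.8 | r=0.5 | r=0.25 | r=0.1 | r=0 |
|---|---|---|---|---|---|
| A | 1.11 | 1.34 | 1.60 | 1.80 | 1.95 |
| B | 1.14 | 1.44 | 1.82 | 2.13 | 2.38 |
| C | 1.17 | 1.56 | 2.08 | 2.52 | 2.90 |

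Take 0.8 or 0.5 as the post-stop rate and 0.25 to 0 as the true on-drug rate. True time divided by modelled time is then:

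| Case | Post-stop r=0.8 | Post-stop r=0.5 |
|---|---|---|
| A | 1.43-1.75 | 1.19-1.46 |
| B | 1.60-2.09 | 1.26-1.65 |
| C | 1.77-2.47 | 1.33-1.86 |

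With d = 0, the case A ratios become 1.47-1.82 and 1.21-1.50.

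In the other direction, using r = 0 when the truth is 0.1 or 0.25 overstates time by 1.09 or 1.22 (A), 1.12 or 1.31 (B), and 1.15 or 1.39 (C).

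**The case against.** The best defence is that the plan commits to neither error. C.4.2 says that "in every treatment month, simulated individuals on therapy will have a probability of developing an ALT or AST elevation", separates the true enzyme level from clinical awareness of it, and gives unidentified patients their own raised risk. C.4.3 opens by preferring trial data where possible and the literature otherwise. Table 4 already takes the probability of symptoms (0.35) from the literature, so the word all was not meant strictly. C.4.5 promises deterministic and probabilistic sensitivity analyses over the model parameters.

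Part of this stands. Entry into the severe state, and movement among asymptomatic states at or below 5x ULN, can come from ADEPTT. The symptom and death exits have literature inputs. What remains is one exit, ALT/AST recovery or persistence on drug. For that exit both the C.4.3 sentence and Table 4 name ADEPTT, and a general fallback does not override a specific assignment. The 0.35 covers only the symptom axis and itself conflicts with the C.4.3 wording. A probabilistic analysis needs a best estimate as its centre, and ADEPTT has none to give here.

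The defence is also right about scale in the first Aim 3 comparison. Per 1000 starters, take 26 onsets (2.6%), all asymptomatic, and mortality of 0.05 per month. The widest contrast (r = 0 versus 0.8) adds 26 × (1.95 − 1.11) × 0.05 = 1.1 deaths in case A and 26 × (2.90 − 1.17) × 0.05 = 2.2 in case C. For TB, Table 4 gives 3.41 cases per 100 person-years and 0.23 case fatality. Five years of cumulative hazard is 5 × 0.0341 = 0.1705. A 30% reduction averts 1000 × 0.23 × [exp(−0.1705 × 0.7) − exp(−0.1705)] = 10 deaths; a 50% reduction averts 17. This assumes full adherence and no competing mortality. On these assumptions no monitoring versus no therapy is not threatened. The comparison among monitoring strategies has no such margin to rely on.

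**Conclusion.** The concern holds. The plan assigns to ADEPTT a parameter that its own stopping rule prevents it from observing, and it acknowledges the effect of that rule only for mortality and utilities. Taken literally, it leaves only off-drug exits to apply to patients modelled as on drug.

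In the illustration, time in asymptomatic >5x ULN is understated by a factor of about 1.2 to 2.5 if post-stop recovery is used, or overstated by about 1.1 to 1.4 if no on-drug recovery is assumed. These figures rest on assumed recovery rates and on Table 4 inputs read with an assumed time unit. The effect on deaths depends on a mortality range that starts at 0, so it can be nil. No change in the ranking of strategies has been shown. Unplanned on-drug time above 5x ULN could occur between visits or through physician judgement, but the time before detection is unobserved and the plan does not rely on it. Aims 1 and 2 are unaffected. The point concerns model inputs only and takes no view on the stopping rule.

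**What to change.** 1. Index the model's transitions by whether the patient is on INH or has stopped.
2. Censor ADEPTT on-drug transitions at INH stop. Use post-stop exits only where the modelled strategy also stops treatment.
3. Take on-drug recovery or persistence from asymptomatic >5x ULN from the literature, or from a wide stated range. Vary it in the deterministic and probabilistic analyses of C.4.5, and report the value at which the preferred strategy changes.
4. Amend the C.4.3 sentence and the Table 4 source for ALT/AST transitions, reconcile both with the literature-based 0.35, and give time units for the Table 4 probabilities.

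The cost is specification wording and a few extra runs of analyses already planned, with no new patient data. The price is a wider uncertainty range for the no-monitoring and week-2 strategies.
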